### **6.2.6 Immunogenicity**

The definitions, summaries and listings described below apply to statistical analysis for anti-BMS-986036 and anti-FGF21 antibodies.

A positive BMS-986036-induced anti-BMS-986036 and anti-FGF21 antibody immunogenicity response is defined as:

1. a missing baseline immunogenicity measurement and a positive laboratory reported immunogenicity response post-baseline
2. a negative laboratory reported baseline immunogenicity response and a positive laboratory reported immunogenicity response post-baseline
3. a positive laboratory reported baseline immunogenicity response and a positive laboratory reported immunogenicity response post-baseline that has a titer value at least 4-fold greater than the baseline titer value

A persistently positive BMS-986036-induced immunogenicity response is defined as post-dose positive results at 2 or more consecutive time-points, where the first and last positive result are at least 16 weeks apart.

Immunogenicity results will be summarized as anti-drug antibody (ADA) negative or ADA positive including persistent positive for anti-BMS-936558 and/or anti-FGF21 antibodies per treatment group in the safety population. The post-baseline evaluable participants and any neutralizing results will also be included in this summary. Figures will be provided to display efficacy endpoints for ADA status. All immunogenicity results will be listed.

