6.3.2.2 Immunogenicity

BMS-986036 is a modified version of human FGF21 and has the potential to be immunogenic; however, the potential safety liability of antibody formation in humans is considered to be low. Most human protein therapeutics can induce a rapid and strong anti-drug antibody (ADA) response in animals, although the presence of ADAs in these species does not necessarily predict immunogenicity in humans.

In the Phase 1 study MB130001, 3 of 72 participants (4%), who received any dose of BMS-986036, developed antibodies to FGF21 and BMS-986036 by the end of the study. An initial assay titer increase was observed, followed by stabilization or decrease in titers, during additional post-study immunogenicity testing over the next 6 months. No participant had persistent positive functional neutralizing ADAs during the Follow-Up Period, although one participant tested positive at 2 nonconsecutive time points. Plasma exposure of BMS-986036 in these 3 participants did not differ from that of other treated participants during the period in which the concentration was detectable. Immunogenicity was not associated with an increased incidence of overall AEs or immunogenicity-related AEs, such as rash or fever, or with altered PK or PD effects.

In Study MB130002, up to Study Discharge (Day 126), anti-BMS-986036 and anti-FGF21 antibodies were detected in 68% and 70%, respectively, of the participants treated with BMS-986036; however, antibody titers were generally low (12.2% and 37%, respectively, had titers ≥ 64), and only 2 participants had neutralizing antibody responses to endogenous

wild-type FGF21. ADAs usually appeared after 8 weeks of dosing and they were not associated with immune-related AEs or injection site reactions. BMS-986036 exposures were similar in participants with ADAs compared with participants without ADAs. During the Follow-Up Period, antibody titers were observed to be either stable or declining in the overwhelming majority of participants, and no participant had neutralizing antibodies.

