7.3 Safety Objective

To demonstrate the safety of BMS-986036 in adults with NASH and compensated cirrhosis throughout the course of the study, including BMD and immunogenicity.

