Participants will be stratified at randomization by country (Non-Japan/Japan). Participants in countries other than Japan will be stratified at randomization according to T2DM status (yes/no). Japanese participants will not be further stratified.

Randomized participants will receive their assigned double-blind study medication for a total of 48 weekly doses. The treatment will be administered by SC injection of 2 pre-filled syringes of study medication in the abdomen according to their assigned treatment arm (see Section 8.4.2). During the Double-Blind Treatment Period (Table 2 in Section 1), participants will be evaluated for safety and efficacy every 4 weeks (\pm 5 days) through Week 24 and every 8 weeks (\pm 5 days) after Week 24 through Week 48.

Participants will then return at Week 52 (\pm 5 days) for a PTFU Visit. Participants who discontinue study medication earlier than Week 48 will have an Early Termination (ET) Visit at the time of study medication discontinuation and will return for a PTFU Visit 4 weeks (\pm 5 days) after the ET Visit.

Participants will return 6 months (\pm 14 days) (1 month is defined as 4 calendar weeks) after the Week 52/PTFU Visit for DXA to assess BMD and for collection of samples for potential immunogenicity testing as well as serum and plasma biomarker samples (see Table 3 in Section 1). Participants at the Week 52/PTFU Visit may need to return at 9 months, 12 months, and 14 months (\pm 14 days) (1 month is defined as 4 calendar weeks) after the Week 52/PTFU Visit if required for immunogenicity testing, as described in Section 8.5.3.6 (see Table 3 in Section 1).

[figure not shown]
Figure 1 Study Design Schematic – Screening to Week 52/PTFU

ET = early termination; PTFU = Post-Treatment Follow-Up; QW = once weekly

^a For participants who discontinue study medication prematurely, liver biopsy will be performed at ET if the participant has completed at least Week 20. If a participant discontinues study participation prior to Week 20 they should consider having a liver biopsy at ET.

Figure 2 Study Schematic – Bone Mineral Density and Immunogenicity Follow-Up Visits After the Week 52/PTFU Visit (visit windows \pm 14 days) (1 month is defined as 4 calendar weeks)

DXA = dual-energy X-ray absorptiometry PTFU = Post-Treatment Follow-Up; QW = once weekly

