8.4.2 Study Medication Administration

Participants should be instructed to make every effort to administer study medication on the same day each week at approximately the same time of day. Each weekly administration will consist of 2 SC injections.

On Day 1 and at the Week 4, 8, 12, 16, 20, 24, 32, and 40 Visits, study medication will be self-administered by the participant or administered by their designee at the study site as part of the participant's scheduled study visits. At those visits, study medication dosing should be held until all study-related assessments, including participant questionnaires, vital signs, ECG, AE evaluation, physical examinations, and laboratory sample collection (including trough [predose] PK) have been completed.

If a study visit occurs on a day that is not a planned dosing day, the participant should continue to administer the medication on the planned dosing day; all study-related assessments will continue to be performed at the planned study visit (in-clinic administration of study drug would not occur).

Study medication is blinded and is supplied in a pre-filled syringe. Each participant will be dispensed a treatment kit containing 2 smaller boxes (for each weekly administration). Each smaller box will contain 1 prefilled syringe of the medication. Both syringes will be administered in the abdominal area at different locations per training guidelines. Study medication will be assigned by the IRT system.

Guidance and training on administration should be given to the participant (or caregiver, if applicable) prior to the first administration. At a minimum, the first administration should be done by the participant under the supervision of qualified site personnel. Training may be repeated as necessary at any study visit at the discretion of the investigator to maintain treatment compliance. When injections are administered at the site during study visits, site staff may observe the injection to ensure proper technique is being employed. Participants will be required to capture the date, time, and location of each injection on the supplied study medication administration card.

Specific instructions for study medication administration as well as training materials for participants (or caregivers, if applicable) are in the Pharmacy Manual.

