8.5.3.6 Immunogenicity

Throughout the study, the potential for immunogenicity of BMS-986036 will be monitored as indicated in the Schedule of Activities (Section 1). In participants that experience immunogenicity, neutralizing activity and exposure-efficacy relationship will be assessed for evidence of a clinical impact on safety and efficacy.

Immunogenicity Assessment Methodology

Participants will be monitored for antibodies to BMS-986036 (drug) using an ADA homogenous bridge assay with electrochemical luminescence detection. Samples will first be screened for potential positive anti-BMS-986036 responses. Then, the samples with positive anti-BMS-986036 responses will be confirmed for specificity using an immunodepletion format with BMS-986036 and nonPEGylated drug. The reactivity of confirmed positive responses will be characterized as “BMS-986036” (specific to the FGF21 region) or “PEG” (specific to the PEGylated region) based on the immunodepletion specificity. Additionally, samples with confirmed positive responses will be titrated to determine the relative positive response.

Participants will also be monitored for antibodies to FGF21 using recombinant Met-FGF21 in a homogenous bridge assay with electrochemical luminescence detection. Samples will first be screened for potential positive anti-FGF21 responses. Then the samples with positive antiFGF21 responses will be confirmed for specificity using an immunodepletion format with wild-type sequence FGF21. Samples with confirmed positive anti-FGF21 responses will be titrated to determine the relative positive response.

Samples positive for anti-BMS-986036 antibodies or positive for anti-FGF21 antibodies will be tested for neutralizing activity in a functional cell based neutralizing antibody assay. The assay measures the ability of an anti-BMS-986036 or anti-FGF21 antibody to inhibit or block Erk1 activation that is induced when FGF21 or drug binds to the β -Klotho and FGF-Rs.

Long-Term Immunogenicity Follow-Up

All participants will have samples collected for immunogenicity at 6 months (\pm 14 days) after the Week 52/PTFU Visit. Samples collected from participants may not be analyzed if: 1) participant is not on active drug, 2) participant is negative for anti-drug and/or anti-FGF21 antibody titers at the Week 52/PTFU Visit, or 3) participant has evidence of stable or decreasing antibody titers for 2 visits prior to the 6-month posttreatment visit.

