#### 4.3.7 Immunogenicity

Immunogenicity (collected at Day 1 and each subsequent visit through the Week 52/PTFU visit and at long-term Immunogenicity Follow-Up visits.

- Proportion of participants with anti-BMS-986036 antibodies (including neutralizing) through Week 52/PTFU and in long-term follow-up

Sponsor: Bristol-Myers Squibb

Protocol No.: MB130-069

- Proportion of participants with anti-FGF21 antibodies (including neutralizing) through Week 52/PTFU and in long-term follow-up

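### In the ADA summary through Week 52/PTFU, late-onset positives and some early stoppers cannot meet the 16-week persistence rule, and no row shows that their follow-up was too short

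*SAP*

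**What the plan says.** SAP 6.2.6 (Immunogenicity) sets two conditions for a persistently positive response: "post-dose positive results at 2 or more consecutive time-points", and a time span, "where the first and last positive result are at least 16 weeks apart". The results table is to show ADA negative and ADA positive participants, with persistent positives identified among the positives. No other subdivision of the positives is defined, and the section does not say up to which visit persistence is judged.

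SAP 4.3.7 states that samples are "collected at Day 1 and each subsequent visit through the Week 52/PTFU visit and at long-term Immunogenicity Follow-Up visits", and it defines the endpoint both through Week 52/PTFU and in long-term follow-up. SAP 7.1 analyses the Week 52 data with a cut-off of 08Oct2020 and describes whatever later data are available. SAP 7.2 places data collected after Week 52/PTFU in a separate later analysis.

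The visits come from protocol 8.4.2 ("On Day 1 and at the Week 4, 8, 12, 16, 20, 24, 32, and 40 Visits") plus Week 48/ET and Week 52/PTFU in Table 2. A participant who stops study medication early has an ET Visit and, per protocol 8.1, "will return for a PTFU Visit 4 weeks (\pm 5 days) after the ET Visit". Protocol Table 3 and section 8.5.3.6 add a sample from every participant 6 months later. That sample may be left unanalyzed under any of three conditions, one being that the "participant has evidence of stable or decreasing antibody titers for 2 visits prior to the 6-month posttreatment visit".

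**The concern.** A duration rule needs enough observation time to be applied. Where the summary period ends less than 16 weeks after the first positive, the response cannot be called persistent, whatever the antibody does. The planned table would place such a participant next to one whose antibody appeared early and then disappeared: both are ADA positive and neither is persistent positive. Short follow-up could then be read as a response that resolved.

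The protocol's safety objective covers safety "throughout the course of the study, including BMD and immunogenicity", so this summary bears directly on a stated objective. If late seroconversion or early stopping differs between arms, the unresolved share will differ too, and a comparison of persistent percentages across doses would partly reflect length of observation. For an earlier study in obese participants with type 2 diabetes, protocol 6.3.2.2 reports that "ADAs usually appeared after 8 weeks of dosing". Onset is therefore not confined to the first visits, although this says nothing about how often it falls at Week 40 or later in this trial.

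**Working it through.** The documents state no figure on this point to reproduce. The check lists the samples and measures the longest span available from each.

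**Inputs.** Post-dose samples at Weeks 4, 8, 12, 16, 20, 24, 32, 40, 48 and 52 (protocol Table 2, 8.4.2; SAP 4.3.7), each visit ±5 days. Month 6 sample: one month is 4 weeks, so 52 + 24 = Week 76, ±14 days (Table 3). Threshold: 16 weeks = 112 days (SAP 6.2.6).

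**1. Participants who complete treatment.** Longest span = 52 − first positive week. The windows can move it by 5 + 5 = 10 days.

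| First positive | Span to Week 52 | Range with windows | At least 112 days? | Span to Month 6 (minimum with windows) |
|---|---|---|---|---|
| Week 32 | 20 weeks | 130–150 days | yes | 44 weeks (40.6) |
| Week 40 | 12 weeks | 74–94 days | no | 36 weeks (32.6) |
| Week 48 | 4 weeks | 18–38 days | no | 28 weeks (24.6) |
| Week 52 | 0 weeks | n/a | no | 24 weeks (22.0) |

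First positivity at Week 32 or earlier can qualify by Week 52. Weeks 40, 48 and 52 cannot, even at the window limits (94/7 = 13.4 weeks at most). All of them can qualify once a Month 6 result is used.

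**2. Early stoppers, by PTFU.** With ET at Week T, PTFU is at T + 4. The rule needs (T + 4) − first positive ≥ 16, so first positive ≤ T − 12.

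| ET at week | First-positive visits that can qualify by PTFU |
|---|---|
| 12 or earlier | none |
| 16 | 4 |
| 20 | 4, 8 |
| 24 | 4 to 12 |
| 32 | 4 to 20 |
| 40 | 4 to 24 |

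The earliest sample is Week 4, so T must be at least 4 + 12 = 16. This uses nominal days; the windows can move the limit by up to 10 days (1.4 weeks). With a Month 6 result, PTFU to Month 6 alone gives 24 weeks (at least 22.0), so any stop time can qualify.

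**3. Whether a Month 6 result will exist.** A participant first positive at Week 40 with stable titers at Weeks 48 and 52 fits the assay exemption in protocol 8.5.3.6. So does one first positive at Week 48, if Weeks 48 and 52 count as the two visits. If the sample is not assayed, the longest span stays at 12 or 4 weeks in the long-term report as well. Someone first positive at Week 52 has a single positive titer and hardly fits the exemption. Participants with rising titers are followed to Month 9 and beyond, so their persistence can be judged.

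**4. Size.** The documents give no distribution of onset times or of early stopping for this trial, so the number affected cannot be derived. For scale, with about 38 participants per arm, all taken as evaluable, one participant is 1/38 = 2.6 percentage points.

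**The case against.** The strongest reply is that sampling does not end at Week 52. Every participant is due a Month 6 sample, protocol 8.3.9.1 expects those who stop medication to attend the immunogenicity follow-up, and 8.5.3.6 offers it to those who leave the study before Week 48. SAP 4.3.7 and 7.2 already plan a long-term report. On this view the Week 52 table is an interim cut that will be completed later. Affected participants also remain in the ADA-positive count and the listings, with neutralizing results summarized, and the SAP defines no transient or not-persistent category.

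Most of this stands, and it rules out several stronger readings:

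- A reader might infer that the visit schedule makes persistence impossible for late-onset positives or for early stoppers in general. It does not: spans to Month 6 are 24 to 36 weeks from Weeks 40 to 52, and stops at Week 16 or later can qualify by PTFU if onset was early enough.
- A reader might infer that the rule errs only towards non-persistence. That holds for short follow-up but not for the whole definition, which does not explicitly exclude negative samples between the first and last positive.
- A reader might take persistence as the plan's main measure of clinical impact. Protocol 8.5.3.6 names neutralizing activity and the exposure-efficacy relationship for that purpose.

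The reply does not remove two points. The period through Week 52/PTFU is reported in its own right without marking who was observed too briefly. The later completion depends on a discretionary assay, and on attendance that participants leaving the study may decline (protocol 8.3.9.2). The exemption covers falling as well as stable titers, so not every unassayed sample hides a continuing response, but stable titers are one of the patterns it covers.

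**Conclusion.** The point holds for the summary through Week 52/PTFU. There the 16-week rule cannot be met by participants first positive at Week 40, 48 or 52, by early stoppers first positive less than 12 weeks before ET, or by anyone stopping before Week 16 on nominal visit days. They appear as ADA positive and not persistent positive, with nothing to separate short observation from a response that ended. The Month 6 sample can correct this, but some late-onset continuing responses may stay unresolved if the assay exemption is used. The documents do not support any estimate of how many participants this concerns.

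This is a minor improvement to a descriptive safety table; no efficacy conclusion depends on it. It rests on the scheduled sampling times and on SAP 6.2.6 being applied as written. Because that section names no data period, using whatever Month 6 data exist at the 08Oct2020 cut-off could also classify identical antibody courses differently according to enrollment date.

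**What to change.** In SAP 6.2.6:

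1. State the data period for persistence: through Week 52/PTFU for the Week 52 analysis, then updated with assayed Month 6 and later samples in the long-term report.
2. Split ADA positives into three mutually exclusive rows, applied in this order:
   - persistent positive, by the current rule;
   - rule not met, last assessed sample positive, and less than 16 weeks from first positive to that sample (persistence not assessable);
   - other positive.
3. Give the persistent percentage over all evaluable participants, and again excluding the second row.
4. Where a Month 6 result exists, use it to reclassify participants in the second row.

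The order matters: a participant positive at Week 40, negative at Week 48 and positive at Week 52 falls in the second row only. Assaying stored Month 6 samples for everyone in that row would resolve more cases, but the change does not depend on it.

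The cost is one paragraph and one extra table row. The same section needs an edit anyway, because its summary sentence names a different compound code (BMS-936558). The downside for the sponsor is a somewhat less favourable persistent or unresolved share.

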## **6.3 Pharmacokinetics**

The PK summaries described in this section will be conducted among the PK population [REDACTED]  
[REDACTED] as appropriate.

### **6.3.1 Serum Concentrations**

Serum concentrations of BMS-986036 will be derived from trough (predose) blood samples collected from each participant before the administration of BMS-986036 dosing at each visit. Trough BMS-986036 serum concentrations (in all participants at all visits) [REDACTED]

[REDACTED] will be summarized by treatment and visit for both C-terminal intact and Total BMS-986036.

Sponsor: Bristol-Myers Squibb

Protocol No.: MB130-069

Serum concentrations below LLOQ will be set to missing in the computation of mean concentration values. Descriptive statistics (n, mean, standard deviation (SD), geometric mean, % coefficient variation (CV), median, min, and max) will be used to summarize the serum concentrations at each scheduled time point.

Linear and semi-logarithmic plots of the geometric mean serum concentrations + SD versus scheduled sampling times, overlaid by treatment will be provided for trough concentrations. [REDACTED]

[figure not shown]
[REDACTED] These plots will show study visit and will include a reference line for LLOQ on all plots with just one analyte. The plots will match the summary table results with the exception for time points with no values >LLOQ. For plotting presentation purposes, for time points with no values >LLOQ a value of one-half LLOQ will be used to plot that time point and a corresponding footnote will be added to indicate which time points were affected. All individual subject serum concentration data will be listed.

In addition, individual participant plots of trough concentrations will be presented for all participants and all scheduled time points among the PK population, with C-terminal Intact and total BMS-986036 concentrations on the same plot.

[REDACTED]

Sponsor: Bristol-Myers Squibb

Protocol No.: MB130-069

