Adiponectin	X	X Samples only to be collected at Week 4, Week 8, and Week 12	X		X	X	See Section 8.5.1 and Table 8 in Section 8.5.4 Participants should fast for at least 8 hours prior to the blood collection for this assessment
Micro RNA (miRNA)	X	X Samples only to be collected at Week 4, Week 8, and Week 12	X		X	X	See Section 8.5.4 and Table 8 in Section 8.5.4
Whole blood for gene expression assessments	X	X Samples only to be collected at Week 4, Week 8, and Week 12	X		X	X	See Section 8.5.4 and Table 8 in Section 8.5.4
Serum for disease, target and drug effect biomarkers	X	X Samples only to be collected at Week 4, Week 8, and Week 12	X		X	X	See Section 8.5.4 and Table 8 in Section 8.5.4. Participants should fast for at least 8 hours prior to the sample collection

Procedure/Assessment	Double-Blind Treatment					Follow-Up	
	Day 1 Visit	After Day 1, up to Week 24 Visits every 4 weeks (± 5 days)	Week 24 Visit (± 5 days)	After Week 24, up to Week 48 Visits every 8 weeks (± 5 days)	Week 48 Visit (± 5 days)/ Early Termination (ET)		
Plasma for disease, target and drug effect biomarkers	X	X Samples only to be collected at Week 4, Week 8, and Week 12	X		X	X	See Section 8.5.4 and Table 8 in Section 8.5.4. Participants should fast for at least 8 hours prior to the sample collection
Trough pharmacokinetic (PK) sampling	X	X	X	X	X	X	Trough (predose) samples will be collected at each visit. See Section 8.5.5

Procedure/Assessment	Double-Blind Treatment					Follow-Up
	Day 1 Visit	After Day 1, up to Week 24 Visits every 4 weeks (± 5 days)	Week 24 Visit (± 5 days)	After Week 24, up to Week 48 Visits every 8 weeks (± 5 days)	Week 48 Visit (± 5 days)/ Early Termination (ET)	
Study Medication						
Study medication administration training	X					Training maybe repeated as necessary at any study visit at the discretion of the investigator to maintain treatment compliance. See Section 8.4
Dispense study medication	X	X	X	X		See Section 8.4
Study medication return/reconcile		X	X	X	X	See Section 8.4

Table 3 Long-Term Bone Mineral Density and Immunogenicity Follow-Up Period Activities – Study MB130-069

Procedure/Assessment	6 Months After Week 52/PTFU (± 14 days) ^a	9 Months After Week 52/PTFU (± 14 days) ^b	12 Months After Week 52/PTFU (± 14 days) ^b	14 Months After Week 52/PTFU (± 14 days) ^b	Notes: 1 month is defined as 4 calendar weeks.

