6.1.2 Clinical Studies

In the first-in-human study (**Study MB130001**), BMS-986036 was administered by subcutaneous (SC) injection in single and multiple doses for up to 14 days to 72 obese, nondiabetic, healthy adult volunteers.¹⁶ C-terminal intact BMS-986036, the active polypeptide, displayed a half-life of approximately 20 - 24 hours and demonstrated a generally linear PK with 2-fold to 3-fold accumulation following QD dosing. Following single dose administration in the range of 1 mg to 60 mg, the drug was slowly absorbed from the SC injection site (abdomen) into the systemic circulation, with median time to maximum concentration ranging from 24 to 33 hours. Following a single weekly dose of 21 mg, the time to maximum concentration was like that of single doses. BMS-986036 in doses of up to 30 mg QD for up to 14 days was well tolerated and safe; adverse events (AEs) were mild and showed no dose-ordered trends. In the multiple-dosing panels, BMS-986036 increased adiponectin levels in a dose-dependent fashion. Adiponectin increased by 41.7% in the BMS-986036 30 mg QD group; in contrast, it decreased by 28.5% in the placebo group. Adiponectin has been shown to inhibit hepatic stellate cell proliferation and hepatic fibrosis in vitro,¹⁷ and higher levels of adiponectin have been shown to correlate with improvements in fibrosis, as well as steatosis and inflammation.¹⁸ It is therefore likely that an increase in adiponectin in response to BMS-986036 would have beneficial anti-steatotic, anti-inflammatory, and anti-fibrotic effects in NASH patients. BMS-986036 also improved insulin sensitivity, promoted favorable lipid changes (decreased TGs, apolipoprotein B, and LDL cholesterol), and reduced body weight compared to placebo.

BMS-986036 was also studied in two Phase 2 studies. **Study MB130002** was a randomized, double-blind, placebo-controlled, parallel-group, multiple-dose study in obese participants with type 2 diabetes mellitus (T2DM). Over 90% of participants had evidence of underlying

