7.4 Pharmacokinetic Objectives

- To determine trough concentrations of BMS-986036 in all participants

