8.3.1 Inclusion Criteria

1. Signed written informed consent
 - a) Participants must be willing to participate in the study and sign the informed consent form(s) (ICF[s])
 - b) Participants (and caregivers as applicable) must be willing and able to complete all study-specific procedures and visits
2. Liver biopsy performed within 6 months (26 weeks) prior to the Screening Period. Biopsy performed prior to ICF must be available to the central reader prior to randomization. If historical biopsy is not available, a liver biopsy will be performed during the Screening Period (see Section [8.5.1.1](#)). Biopsy must be consistent with NASH and cirrhosis according to the NASH CRN classification, as assessed by the central reader.
3. Participants taking anti-diabetic, anti-obesity, or anti-dyslipidemic medications must have been on stable regimens for at least 3 months (12 weeks) (6 weeks for statins) prior to and during the Screening Period. The investigator may contact the medical monitor regarding the stability of a participant's regimen when determining eligibility for study participation. Participants taking vitamin E at doses ≥ 800 IU/day must have been on stable doses for at least 6 months (26 weeks) prior to and during the Screening Period. Vitamin E treatment (≥ 800 IU/day) must not have been initiated after the qualifying liver biopsy was performed.
4. Age and reproductive status
 - a) Men or women 18 to 75 (inclusive) years of age
 - b) Women of childbearing potential (WOCBP) must have a negative pregnancy test (minimum sensitivity 25 IU/L or equivalent units of human chorionic gonadotropin) within 24 hours prior to the start of study medication
 - c) Women must not be breastfeeding at any time during the study

- d) WOCBPs must agree to follow instructions for method(s) of contraception for the duration of treatment (BMS-986036 or placebo) plus 5 half-lives of study medication (5 days) plus 30 days (duration of ovulatory cycle) for a total of 35 days after the end of the Double-Blind Treatment Period
- e) WOCBPs who are continuously not heterosexually active are exempt from contraceptive requirements but must undergo pregnancy testing as described in the Schedule of Activities in Section 1

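### SAP 6.3.1 summarises samples from every visit as trough with no visible time-since-dose rule, so visits off the weekly dosing day contaminate the by-visit trough tables, mostly upward

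*SAP*

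**What the plan says.** The only stated PK objective (Protocol 7.4) is "To determine trough concentrations of BMS-986036 in all participants". The Schedule of Activities (Table 2) says "Trough (predose) samples will be collected at each visit", and Protocol 8.1 gives on-treatment visits a window of 5 days either side.

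Protocol 8.4.2 asks for injections on the same day each week. On a visit day the dose is held until the assessments are done, and the predose PK sample is named among them. If the visit is not on a dosing day, the injection stays on its planned day and "all study-related assessments will continue to be performed at the planned study visit (in-clinic administration of study drug would not occur").

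SAP 6.3.1 describes samples drawn before dosing at each visit and summarises "Trough BMS-986036 serum concentrations (in all participants at all visits") by treatment and visit, for C-terminal intact and Total drug. Values below the quantification limit are set to missing in the means. SAP 5.0 admits to the PK population anyone with a dose and any concentration data. SAP 8.3 keeps an assessment at its recorded planned visit even when it was out of window. Text is redacted next to the SAP 6.3.1 sentence, in the SAP 6.3 lead-in and in the PK population definition.

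**The concern.** Holding the dose on visit days yields a trough only when the visit falls on a dosing day. Otherwise the protocol itself directs a sample at some other point in the weekly cycle, and the visible SAP text reports it as a trough. For a drug with a half-life near one day and a 7-day interval, a shift of one or two days matters.

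Trough is also the exposure scale of the dose rationale: Protocol Table 4 predicts biomarker responses at trough. Protocol 6.2.1 says Phase 3 dose selection will draw on this study's PK. At stake is whether a by-visit trough mean reflects the dosing regimen or partly reflects when people came to clinic.

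**Working it through.** **Inputs.** Protocol 6.1.2: C-terminal intact drug "displayed a half-life of approximately 20 - 24 hours", "median time to maximum concentration ranging from 24 to 33 hours", and "2-fold to 3-fold accumulation following QD dosing". Protocol 8.3.1: "5 half-lives of study medication (5 days"). Dosing interval 168 h; visit window 5 days either side.

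**The plan's own figures.** Five half-lives are 5 × 20/24 = 4.2 days to 5 × 24/24 = 5.0 days, which reproduces the stated 5 days at 24 h. Daily-dosing accumulation is 1/(1 − 2^(−24/t½)) = 1.77 at 20 h and 2.00 at 24 h, so it meets only the lower edge of the stated 2- to 3-fold.

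**Time since dose.** A visit d days early is 7 − d days after the last injection. A visit d days late is d days after it, because the injection was given on its planned day.

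**Ratio to the 168 h trough.** The simple form is 2^((168 − h)/t½), with h the hours since dose. Because absorption is slow, a one-compartment model with first-order absorption was also run at weekly steady state, with the absorption rate solved from a time to peak of 24-33 h.

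| Days since dose | How it arises | Simple decline | With absorption |
|---|---|---|---|
| 6 | 1 early | 2.0-2.3 | 1.7-2.2 |
| 5 | 2 early or 5 late | 4.0-5.3 | 3.0-4.8 |
| 4 | 3 early or 4 late | 8-12 | 4.9-10 |
| 3 | 4 early or 3 late | 16-28 | 7.6-20 |
| 2 | 5 early or 2 late | 32-64 | 10-36 |
| 1 | 1 late | 64-147 (unreliable, near peak) | 11-48 |

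The absorption column is the one to use. If the true accumulation were 3-fold, the decline would be slower: 1/(1 − x) = 3 gives x = 2/3 per day. Simple-decline ratios would then be 1.5 per day of shift: 1.5 at day 6, 2.25 at day 5 and 1.5^5 = 7.6 at day 2.

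**Week 48.** The 48th weekly dose falls on Day 1 + 47 × 7 = 330. The visit is Day 337, and Protocol 8.4.2 lists no in-clinic dose there. Time since dose is therefore 7 ± 5 = 2 to 12 days. With no further dose, the model gives 0.45-0.56 at day 8 and 0.02-0.05 at day 12.

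**Samples that are not troughs by design.** Day 1 precedes any drug. Week 52 (Day 365) is 365 − 330 = 35 days after the last scheduled dose.

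**Effect on a summary.** The off-day share q is not in the documents; take q = 10% inflated r-fold. The arithmetic mean is multiplied by 1 + q(r − 1): 1.4 at r = 5 and 2.9 at r = 20. The geometric mean is multiplied by r^q: 1.17 at r = 5 and 1.35 at r = 20. If instead every off-day visit is one day early (r = 2), 10-30% off-day gives 1.1-1.3 and 1.07-1.23.

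**The case against.** Much of the case on the other side stands. Nominal visits fall on multiples of 7 days and participants inject on a fixed weekday, so visits kept to plan give true troughs. Table 9 ties its visible predose samples to dosing days, though redaction hides whom it covers. A sample-eligibility rule may sit in the redacted text, so one can say only that no rule is visible. The half-life comes from obese, nondiabetic healthy volunteers and is for C-terminal intact drug; none is given for Total. Missed doses push samples below trough. The mean plots use geometric means and medians are tabulated, and both resist contamination better than the arithmetic mean. All concentrations are listed. A population PK model may derive individual troughs, but it is optional and reported outside the clinical study report, so it does not repair the SAP tables.

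A reader might infer three stronger things that the documents do not support.

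- **That the PK objective goes unanswered.** On-day samples answer it, and the off-day share is unknown.
- **That dose ratios are biased.** All arms share one blinded visit schedule. With roughly linear PK and similar off-day shares, the inflation is about the same in each arm, which adds noise but gives no mechanism for a distorted ratio.
- **That an apparent antibody effect on exposure could be an artefact.** No visible SAP table compares trough by antibody status. SAP 6.2.6 plots efficacy by that status, and immunogenicity effects on PK are left to the population model.

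Week 52 has its own visit row, so there the problem is only the label.

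**Conclusion.** The concern holds as a defect in the definition of the trough summaries. Followed as visibly written, the protocol and SAP place off-dosing-day samples in tables and plots headed trough. For C-terminal intact drug each such sample is off by about 2-fold (one day early) to tens-fold, mostly upward, with late Week 48 samples below trough. The dose range is 4-fold (10 to 40 mg), so the error in a single sample can match it. Setting values below the quantification limit to missing may add upward bias, since true troughs are more likely to drop out than off-day samples.

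The factors rest on one-compartment kinetics, steady weekly dosing and the healthy-volunteer half-life; slower effective decline would shrink them. The effect on any reported mean cannot be fixed without the off-day share, and the 10% used here is an assumption. These are descriptive summaries with no hypothesis test, and the primary endpoint is untouched. The change is still worth making because trough is the sole stated PK objective.

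**What to change.** In SAP 6.3.1:

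- Derive actual time since the last injection from the dosing record and the PK sample date and time.
- Restrict the trough tables and mean plots to samples drawn before the next dose and within a narrow prespecified window around 168 h. Plus or minus 12 h admits about 0.67-1.5 times trough under the model above. A 6-8 day window would admit 0.45-2.2 times, a spread of up to about 5-fold within one parameter setting (2.2/0.45), so it should not stand alone. If only dates are available, use the wider window with a sensitivity summary.
- Report the number excluded by arm and visit.
- Keep every sample in the listings and, with actual times, for population PK.
- Label Day 1 as pre-treatment and Week 52/PTFU as post-treatment washout.
- If the redacted text already holds such a rule, refer to it in the visible text.

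The cost is SAP wording and programming. Participants record the date and time of each injection on the administration card (Protocol 8.4.2), and SAP 6.5.6.1 lists exposure by injection. Whether clock times reach the database is not stated. The downside is a smaller n per visit in the trough tables.
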